# 6.2.2 ENDOVASCULAR TREATMENT/PROCEDURE

Once all inclusion/exclusion criteria have been satisfied, including imaging assessments, the subject will proceed with the mechanical thrombectomy procedure using the FlowTriever2 Catheter.

Sites will complete the procedure per standard institutional guidelines and physician discretion. The procedure requirements from the IDE-specific IFU for the use of the FlowTriever 2 Catheter are listed below. Refer to the IDE-specific IFU for more information on the appropriate use of the device for this study.

- Administer IV sedation or general anesthesia, as appropriate, to assure subject comfort and safety.
- Administer/continue to administer anticoagulation medications per standard institutional guidelines.
- Access the target area via femoral or jugular vein per standard institutional guidelines for thrombectomy procedures.

# For use in Pulmonary Arteries:

- Place an exchange length 0.035" guidewire into the target vessel through the right atrium and into the target pulmonary artery.
- Using angiographic radiography, determine the location and size of the area to be treated.
- Verify that the guidewire extends beyond the treatment area.
  - WARNING: Do not treat vessels smaller than 6 mm diameter.
- Refer to the respective Instructions for Use (IFU) for Triever Preparation. Prepare and insert the Triever20 or Triever24.Attach the "Y" connector to the proximal Luer connector by sliding over the FlowTriever2 Catheter shaft.
- Flush the Delivery Catheter through the stopcock with sterile saline to remove all air. Tighten the rotatable hemostatic valve. Close stopcock.
- Place the FlowTriever2 Delivery Catheter containing the collapsed FlowTriever2 element over the guidewire, through the Triever Catheter, and advance through the target clot.
  - WARNING: Avoid using excessive force to advance or retract against resistance. If excessive resistance occurs, retract, and collapse the distal element into the catheter and remove the device. Excessive force against resistance may result in damage to the device or vessel perforation.
- Pin the guidewire. While maintaining the Triever Catheter and FlowTriever2 Catheter position, manually retract the FlowTriever2 Delivery Catheter enough to allow the self-expanding element to expand within or beyond some portion of the clot.
  - The proximal and distal ends of the element contain a radiopaque marker to aid in maintaining proper position as the FlowTriever2 Delivery Catheter is retracted.
- Lock the FlowTriever2 Catheter and the Delivery Catheter together by tightening the Tuohy-Borst connector.
- Manually retract the FlowTriever2 Catheter inside the Triever Catheter to capture the targeted thrombus.
- Remove the FlowTriever2 Catheter from the Triever Catheter while maintaining the position of the Triever Catheter and guidewire. Depress the buttons on the Triever Catheter hemostasis valve as the FlowTriever2 element passes through the valve septum.
- Perform aspiration via the Triever Catheter side port using the 60-cc syringe provided in the package to capture additional thrombus. This step can be performed before and/or after the manual FlowTriever2 Catheter retraction.
- If thrombus remains, repeat steps 4-9.
  - Caution: If the same FlowTriever2 Catheter device is used for another pass, the FlowTriever2 Catheter device and element should be thoroughly examined for damage and rinsed to prevent the introduction of thrombus to the patient.

FLARE-FT2 Study CONFIDENTIAL Page 32 of 60

- After the procedure is complete, remove the Triever Catheter and FlowTriever2 Catheter from the patient.
- Complete the procedure per standard institutional guidelines for thrombectomy procedures.

The FlowTriever System, including the FlowTriever2 Catheter, must be the only device used for thrombectomy. Additional adjunctive drugs may be used at the discretion of the Investigator. Post-procedure, the Investigator will review all images, clinically assessing the PE status and looking for evidence of vessel injury (perforation/dissection). An Inari Medical representative may be present during the thrombectomy procedure.

Procedure assessments will include the following:

- Invasive PA pressure (pre- and post-procedure)
- Record concomitant medications
- Record adverse events, as applicable

# 6.2.3 48-HOUR FOLLOW UP (+36 HOURS, OR AT TIME OF DISCHARGE, WHICHEVER COMES FIRST)

The sites will complete the following assessments on the subjects at the 48-hour visit or at time of discharge, whichever comes first:

- Physical examination and vitals
- Record adverse events, as applicable
- Record concomitant medications

\*Note: If discharged prior to 48 hours from Index Procedure, phone call to subject will be conducted to confirm if any SAEs occurred between time of discharge and 48 hours.

# 6.2.4 30-DAY VISIT (-5 TO + 15 DAYS)

The sites will complete the following assessments either remotely or in-person on the subjects at the 30-Day Visit (visit window = 30 days from procedure -5 days / +15 days):

- Physical examination and vitals
- Record adverse events, as applicable
- Record concomitant medications
- Complete Study Exit form

If the 30-Day Visit is completely remotely, the physical examination and vitals are not required.

Subjects who expire during their participation will be documented on an Adverse Event form and Study Exit form. Sites will fill out the Study Exit form for all enrolled subjects, regardless of reason, at the 30-Day Visit.

# 6.2.5 UNSCHEDULED VISITS

The unscheduled assessments should be done as clinically indicated and corresponding data must be documented on the case report forms and submitted to the Sponsor. The study will only record patient visits during the follow-up period that are related to the patient's PE condition and treatment including:

- Physical examination/vitals
- Concomitant medications
- Adverse events

FLARE-FT2 Study CONFIDENTIAL Page 33 of 60

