#### 3.4 FLASH INTERIM STUDY RESULTS

An interim analysis of outcomes out to 30 days on the first 250 subjects was recently published. 63 These subjects (60.9 ± 13.9 years, 52.4% male) were enrolled across 19 sites, with 93.2% having intermediate-risk PE and 6.8% high-risk PE. The average baseline RV/LV ratio was 1.5 ± 0.5 and sPESI was 1.6 ± 1.1. Elevated biomarkers were present in 96.2% of subjects, and 68.4% of subjects had concomitant DVT. The primary endpoint of composite MAEs occurred in three (1.2%) subjects, all of which were non-ICH major bleeds, and no deaths (0.0%) occurred within 48 hours.

In-hospital outcomes demonstrated significant improvements across several acute parameters. Subjects experienced significant on-table hemodynamic improvements, including a 22.2% decrease in mean pulmonary artery pressure (31.9 mmHg to 24.8 mmHg, P < 0.001) and a 13.3% increase in cardiac index in subjects with a low baseline cardiac index (1.7 to  $1.9 \text{ l/min/m}^2$ , P = 0.005). There was only one (0.4%) access site complication. The median post-procedure hospital length of stay was 3.0[2.0 - 5.0] days and ICU length of stay was 0.0[0.0 - 1.0] days.

Thirty day follow up data was available for 242 subjects in this analysis. In this population, there was one death (0.4% allcause mortality), which was unrelated to the device, and there were 13 hospital readmissions, only one of which was related to the patient's acute PE. The average RV/LV ratio improved by 28.3% at follow up (P < 0.001) and subjects with confirmed baseline dyspnea had a significant improvement from baseline to 30 days (Modified Medical Research Council Dyspnea Scale,  $2.9 \pm 1.1$  to  $0.8 \pm 1.1$ , P < 0.001).

**CONFIDENTIAL** Page 23 of 60 FLARE-FT2 Study

These interim results of the FLASH all-comer registry demonstrate both safety and efficacy of the FlowTriever System, with a low all-cause mortality rate (0.0% at 48 hours, 0.4% at 30 days; no device-related deaths), along with significant and immediate hemodynamic improvements and continued improvements in RV/LV ratio and dyspnea out to 30 days.

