# 8 ADVERSE EVENT AND PRODUCT COMPLAINT RECORDING/REPORTING

Subject safety is of the utmost importance. Each Investigator has the responsibility for the safety of the subjects under his/her care. For purposes of understanding data and relevant confounders, assessment of clinical outcomes and/or SAEs possibly related or probably related to PE condition or complications thereof will be recorded.

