## 8.2 ADVERSE EVENTS (AE)

An Adverse Event (AE) is any untoward medical occurrence, unintended disease or injury, or untoward clinical signs (including abnormal laboratory findings) in subjects, users or other persons, whether or not related to the investigational medical device and whether anticipated or unanticipated. (ISO 14155:2020 3.2)

- **NOTE 1:** This definition includes events related to the investigational medical device or the comparator.
- **NOTE 2:** This definition includes events related to the procedures involved.

**NOTE 3:** For users or other persons, this definition is restricted to events related to investigational medical devices or the comparator.

Disease signs and symptoms that existed prior to study participation are not considered AEs unless the condition recurs after the subject has recovered from pre-existing condition, or the condition worsens in intensity or frequency during the study.

Collection of adverse events will start after the time that informed consent form is signed and subject is enrolled. Adverse events will be monitored throughout the study. Investigators must obtain all information available to determine the causality and outcome of the AE and to assess whether it meets the criteria for classification as a serious adverse event requiring immediate notification to the Sponsor or its designated representative. All reported AEs will be documented on the appropriate CRF and will include the event description (sign, symptom, or diagnosis), onset, resolution, seriousness, severity, cause and action taken. The Investigator must assess causality and severity for all AEs.

All AEs will be followed by the Investigator until resolution or until the 30-day follow-up visit.

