#### 8.5 ADVERSE EVENT REPORTING

Subjects will be carefully monitored during the study for possible adverse events. Any adverse event that occurs after the time of informed consent and a study specific exam or procedure through end of study participation will be fully evaluated by the Investigator. Appropriate treatment will be initiated, and the study follow-up will continue as completely as possible.

The Investigator will document all observations and clinical findings of adverse events, including the nature, severity and relationship, on the appropriate CRFs.

The Investigator is required to report all UADEs/USADEs to the Sponsor within 24 hours after first learning of the event, and all SAEs within 5 business days after learning of the event. The Investigator must follow their local IRB policy for SAE/UADE/USADE reporting.

The Investigator will send the completed SAE Report form and all available supporting documentation to the Sponsor.

As additional information becomes available, the Investigator will record all adverse events (serious and non-serious), adverse device effects (anticipated and unanticipated), device malfunction, product complaints or other reportable safety events on the appropriate CRFs. Copies of source documentation which contain significant information related to the event such as progress notes, consultations, nurse's notes, operative reports and patient summaries etc. are required for evaluation of the event. Copies of such documentation shall be obtained from the Investigator (de-identified as to the Subjects' identity) and provided to the Sponsor.

Regarding subject deaths, it is requested that a copy of the death certificate and a copy of the autopsy report, if applicable, be sent to the Sponsor when available. Any other source documents related to the death should also be provided to the Sponsor. In the event that no source documents are available, the PI is required to describe the circumstances of the Subject's death in a letter, e-mail or other written communication.

UADEs/USADEs have special reporting requirements. The Sponsor will notify the sites, IRBs and regulatory bodies as per specific regulations.

In addition, the Sponsor will comply with Medical Device Reporting (MDR) requirements.

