## 8.7 CLINICAL EVENTS COMMITTEE

A Clinical Events Committee (CEC), an independent group of individuals knowledgeable in the appropriate medical specialties pertinent to the disease state being evaluated in this Study, will be responsible for the review and validation of all adverse events that occur over the course of the Study and the subsequent classification of these events as related to the device or procedure. The CEC will review and adjudicate all adverse events according to the CEC Charter; they can request additional source documentation and any imaging obtained in support of the adverse event to assist with adjudication. The CEC adjudicated results will overrule Investigator assessments.

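### Section 6.2.5 restricts recorded unscheduled visits to those related to PE and its treatment, which conflicts with the all-event recording and adjudication rules in 8.2, 8.5 and 8.7 and could let a misattributed post-discharge event miss the CEC

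*Protocol*

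**What the plan says.** Two places in the protocol tie recording to relatedness.

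- Section 6.2.5 (Unscheduled Visits): "The study will only record patient visits during the follow-up period that are related to the patient's PE condition and treatment". The list that follows covers physical examination, concomitant medications and adverse events, so the restriction reaches event data as well as the visit itself.
- Section 8, opening paragraph: "assessment of clinical outcomes and/or SAEs possibly related or probably related to PE condition or complications thereof will be recorded". The stated purpose is to help interpret the data and confounding.

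Three places set an unrestricted rule.

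- Section 8.2 defines an AE "whether or not related to the investigational medical device and whether anticipated or unanticipated" and adds: "All reported AEs will be documented on the appropriate CRF".
- Section 8.5 has the investigator evaluate "Any adverse event that occurs after the time of informed consent and a study specific exam or procedure through end of study participation", record serious and non-serious events alike, and report every SAE to the sponsor within five business days.
- Section 8.7 gives the CEC all adverse events to adjudicate and then states: "The CEC adjudicated results will overrule Investigator assessments".

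The endpoints at issue are the 30-day secondary safety endpoints in sections 4.4 and 9.5, which are defined as adjudicated events: all-cause mortality, device-related SAE and symptomatic recurrent PE.

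**The concern.** A site cannot follow 6.2.5 literally and also follow 8.2 and 8.5. Take an emergency visit or readmission on day 12 that the site considers unrelated. Section 6.2.5 says not to record it. Section 8.5 says to record any adverse event seen there and, if it is serious, to report it. Under section 8.2.2 an in-patient hospitalization generally makes the event serious.

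The order of the decisions matters. The CEC exists so that relatedness is not left to an investigator who knows that every subject received the device. If the site's own relatedness call decides whether the visit is recorded, that call comes before adjudication, and the CEC can correct it only for events that still arrive by another route. A filter of this kind can lower the adjudicated 30-day rates but cannot raise them, and events that were not collected cannot be recovered at analysis.

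**Working it through.** **1. The plan's own figure.** The only sample-size figure is at least 80% power with N = 50, 11% against a 25% performance goal, one-sided alpha 0.05 (Protocol 9.1, SAP 5.1). The exact binomial test rejects at 7 or fewer events: P(X ≤ 7 | 0.25) = 0.0453 and P(X ≤ 7 | 0.11) = 0.8207. The figure reproduces. It concerns the primary safety endpoint, and nothing below depends on it.

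**2. Which events are exposed.**

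| Event | Other capture route | Exposed to the 6.2.5 wording? |
|---|---|---|
| Primary safety components, during the procedure or to 48 hours | Procedure record; 48-hour or discharge visit; phone call about any SAE if discharged early (6.2.3, Table 1 footnote) | Essentially no |
| Death | AE form and Study Exit form for every death during participation (6.2.4) | Essentially no |
| Later event recognised as device- or procedure-related | Passes 6.2.5 through the word treatment; also 8.5 | No |
| Recurrent PE recognised as such | PE-related by definition (section 12) | No |
| Later device-related SAE or recurrent PE that the site attributes to something else | 8.2 and 8.5; AE collection at the 30-day visit; monitoring against medical records (10.9) | Yes, if 6.2.5 is followed literally and these routes also miss it |

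The last row is the whole exposure. The 30-day visit is a real but partial safeguard. It may be remote and without examination (6.2.4), and a subject can be classed as lost after a minimum of two contact attempts (6.3). For such a subject an unscheduled visit may be the only source.

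**3. Can the undercount be sized?** No. The calculation needs a true 30-day device-related SAE rate r and a capture fraction c, and the documents give neither. The following is an illustration under assumed values, with N = 50. The 11% is borrowed from the primary safety assumption; 2% and 5% are arbitrary. Expected recorded cases = 50 × r × c, and the chance of recording none = (1 − r × c)^50.

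| Assumed r | c = 100% | c = 75% | c = 50% |
|---|---|---|---|
| 2% | 1.0 (0.364) | 0.75 (0.470) | 0.5 (0.605) |
| 5% | 2.5 (0.077) | 1.88 (0.148) | 1.25 (0.282) |
| 11% | 5.5 (0.003) | 4.12 (0.013) | 2.75 (0.059) |

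Cells show expected recorded cases, with the chance of recording none in brackets. Full capture is what 8.2 and 8.5 require, and there the loss is zero. Each subject missed moves a rate in 50 subjects by 1/50 = 2 percentage points.

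**4. Workload of the remedy.** In FLASH (section 3.4), among 242 subjects with 30-day data, "there were 13 hospital readmissions, only one of which was related to the patient's acute PE". Scaled to this study, 13/242 × 50 = 2.69 readmissions, of which 12/242 × 50 = 2.48 were not related to the acute PE. This sizes the extra forms. It does not size missed device-related events, for the reasons given under the objection.

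**The case against.** The strongest reply is that 6.2.5 governs which visits are recorded and does not cancel the separate duties about events. Sections 8.2, 8.5 and 8.7 cover all adverse events. The relationship scale in 8.4 has concomitant-disease, unrelated and unknown categories, which would serve little purpose if unrelated events were meant to be dropped. The 30-day visit collects events without a relatedness condition. For an event to be lost, the site must misattribute it and fail to report it despite 8.5, and the 30-day contact and monitoring must both miss it. The endpoints are also descriptive and do not determine study success (SAP section 2).

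Most of this stands, and it rules out several stronger readings that a reader might infer.

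- *Section 8 limits recording to PE-related SAEs.* Its opening sentence contains no such restriction. It is introductory and sits above operative rules that cover everything.
- *12 of 13 readmissions, or 92%, would go unrecorded.* FLASH counted readmissions unrelated to the acute PE, whereas 6.2.5 also admits visits related to treatment. An unplanned readmission for an adverse event is in any case reportable under 8.5. FLASH therefore estimates neither unrecorded visits nor missed device-related SAEs. In FLARE (section 3.1), none of the SAEs in the additional 10 patients with events by 30 days was judged device- or procedure-related.
- *Bleeds after discharge but within 48 hours would be missed.* The phone call asks about any SAE in that interval.

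The objection does not remove the contradiction. Section 6.2.5 is the specific instruction for the setting in which post-discharge events appear, it names adverse events, and nothing in it says that section 8 takes precedence.

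**Conclusion.** The protocol gives conflicting instructions on recording post-discharge events. Read literally, 6.2.5 places an unblinded relatedness judgement ahead of CEC adjudication for the 30-day secondary safety endpoints. These endpoints could be undercounted, chiefly device-related SAE, and recurrent PE if it is misattributed. The documents do not support saying that they are undercounted. The size is unknown, and it is zero where sites follow 8.2 and 8.5. The primary safety endpoint, mortality, N and power are essentially unaffected. Severity is minor to moderate: the exposure is narrow, but it concerns the completeness of adjudicated safety data and is easily removed.

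This rests on two assumptions: that some sites would treat 6.2.5 as the controlling rule for unscheduled visits, and that the 30-day contact and monitoring would not always recover what was left out.

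**What to change.** Reword 6.2.5 to say that all unscheduled, emergency and inpatient visits involving an AE or SAE, through the 30-day contact, are recorded whatever the site's view of relatedness, and that every AE and SAE goes to the CEC. Align the opening of section 8 with 8.2, 8.5 and 8.7, either by removing the relatedness qualifier or by stating that it does not limit AE or SAE recording.

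The cost is two sentences of protocol text and a few additional visit and AE forms: about 2 to 3 readmissions in 50 subjects at the FLASH rate. Emergency visits without admission would add to this, but the documents give no figure from which to estimate them. Sample size and the analysis do not change.

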### 6.3 HANDLING OF LOST TO FOLLOW-UP SUBJECTS

Every attempt must be made to have all subjects complete the follow-up visit schedule. A subject will be considered lost-to-follow-up when all efforts to obtain compliance are unsuccessful. At a minimum, the effort to obtain followup information must include two attempts to make contact and must be documented in the subject's medical records and appropriate study records.

#### 6.4 STUDY DISCONTINUATION

The Sponsor and applicable regulatory authorities have the right to terminate the entire study or study activities at an individual site at any time. The circumstances which may warrant study termination include, but are not limited to:

- Increased incidence of adverse experiences and/or the severity of such, suggestive of a potential, device-related health hazard, or
- Insufficient subject enrollment rates, or
- Recurrent protocol deviations or other non-compliances, or
- Inaccurate, incomplete, and/or untimely data recording on a recurrent basis, or
- Lack of cooperation with monitoring visits (e.g., failure to adequately prepare for visits, address action items from one visit to the next, or provide access to medical records)

# Study Discontinuation by IRB

The IRB may choose to discontinue the Study at any center(s) for which they granted approval if the:

- Research study is not conducted in accordance with the IRB's requirements
- Research study indicates unexpected serious harm to subjects

### Study Discontinuation by Sponsor

The Sponsor may choose to discontinue the Study should the Sponsor discover additional information during the Study that may cause harm to subject safety. If the Study is terminated or suspended, the Sponsor will promptly inform all Investigators of the termination or suspension and the reason(s) for this. The IRB will also be informed, either by the Sponsor or Investigator if a local IRB is utilized, promptly and provided with the reason(s) for the termination or suspension. If applicable, regulatory authorities will be informed.

